9.2 Findings Identified During Follow-up

Any infant noted to have abnormal or clinically suspicious findings on physical exam, growth monitoring and/or testing will be provided with or referred to local providers of pediatric care. Note, all women, upon enrolling in the study, will receive referrals for prenatal care if they are still pregnant. In the case of HIV drug resistance mutation testing, the IoR/designee will make reasonable efforts to furnish a written copy of the results to the infant's care provider, with permission of the parent(s) or guardian, as applicable. In the case of identified structural anomalies and/or potential deviations from normal health, the IoR/designee will make every effort to communicate directly with the referral entity, provided that consent has been obtained for this purpose.

10 STATISTICAL CONSIDERATIONS

10.1 Overview and Summary of Design

This is a prospective observational cohort study of pregnant women and their infants identified in microbicide trials conducted by the MTN. Infants will be followed for 12 months. Infants from multiple-birth pregnancies are eligible for enrollment. Participants and their infants can be enrolled for subsequent pregnancies and will need to be reenrolled into EMBRACE.

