5.1 Selection of the Study Population: Mother

Recruitment

Potential participants will be recruited for EMBRACE as soon as possible after identification of pregnancy. Participants and their infants can be enrolled for subsequent pregnancies; subsequent pregnancies of an EMBRACE participant will require a separate informed consent process to be initiated. With assistance from the SDMC, the Site Investigator of Record (IoR) or designee will identify participants who become pregnant during participation in parent microbicide trials.

Retention

Each site will establish participant retention procedures. Study site staff members at each site are responsible for developing and implementing site-specific standard operating procedures (SOPs) to target high rates of retention.

Co-Enrollment Guidelines

Co-enrollment in other trials not involving investigational agents is permitted by this protocol. Co-enrollment in EMBRACE and studies of investigational agents (other than the parent protocol) will be considered on a case-by-case basis and must be approved by the Protocol Chair(s). However, it is expected that the Protocol Chair will permit co-enrollment in studies of potential benefit to the mother or baby including prevention of mother-to-child transmission (PMTCT) and/or adult or infant treatment of HIV infection.

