10.7 Data Analysis

In most cases, the analyses will be stratified by parent protocol. However, when appropriate, analyses combining data from multiple protocols may be conducted. When the use of descriptive statistics to assess group or site characteristics or differences is required, the following methods will be used: for categorical variables, the number and percent in each category; for continuous variables, the mean, median, standard deviation, quartiles and range (minimum, maximum). Typically, within-arm assessment of the change from the baseline measurement to a follow-up measurement will be analyzed using McNemar's test (for categorical response variables) or the paired t-test or Wilcoxon signed-ranks test (for continuous variables). In general, when use of formal testing to assess differences between study arms is required, the following methods will be used: for binomial response variables, chi-square tests (or Fisher's exact test, if appropriate) and logistic regression; for continuous variables, t-tests and linear regression, or nonparametric methods if data are non-Normal. To assess baseline differences between study arms, participants will be compared for baseline characteristics including demographics and laboratory measurements using descriptive statistics.

The proportion of participants with adverse pregnancy and delivery outcomes (as specified in Section 10.2.1) will be compared by study arm using a Fisher exact test or chi-square test, depending on the prevalence, with a two-sided level of significance. The proportions of major malformations observed in infants will be compared using the same methods.

For each of the growth parameters (i.e., birth weight, serial length, weight, and head circumference), the mean observed in the active agent and non-active agent groups will be compared using a Student's *t*-test at selected time points: birth, one, six, and 12 months. More generally, GEE (generalized estimating equation) methods and robust variance estimates will be used to evaluate group differences over the first year. Incomplete data from infants that are lost to follow-up or terminate early in the study

(including from death) will be included in these analyses if a growth parameter is available at one of the selected time points.

Among infants who acquire HIV-1 infection, the proportion of infants with HIV-1 drug resistance mutations will be compared by study arm using Fisher's exact test with a two-sided level of significance.

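### Section 10.7 ignores correlation between records of the same mother, so chi-square, logistic and t-test p-values may be mildly too small

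*Protocol*

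**What the plan says.** Protocol Section 5.1 allows a woman to be enrolled again for a later pregnancy. The only condition attached is administrative: "subsequent pregnancies of an EMBRACE participant will require a separate informed consent process to be initiated". Section 10.1 repeats the permission and extends it to twins and higher multiples: "Infants from multiple-birth pregnancies are eligible for enrollment. Participants and their infants can be enrolled for subsequent pregnancies".

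Section 10.7 then names the tests. Adverse pregnancy and delivery outcomes "will be compared by study arm using a Fisher exact test or chi-square test, depending on the prevalence, with a two-sided level of significance". For infants, "The proportions of major malformations observed in infants will be compared using the same methods". The general rule for binary data is "for binomial response variables, chi-square tests (or Fisher's exact test, if appropriate) and logistic regression". Mean growth is compared between groups by Student's t-test at birth and at one, six and 12 months. GEE with robust variance is added for group differences in growth over the first year, but the section does not say whether the cluster is the infant or the mother.

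No passage limits the analysis to one record per woman or one infant per pregnancy, and none clusters on mother. Section 10.7 describes the maternal comparison as a proportion of participants. This leaves open whether a woman enrolled for two pregnancies counts once or twice.

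**The concern.** Twins share a mother, a pregnancy and a parent-trial arm. Two pregnancies of one woman within the same parent trial share her arm and her underlying risk. Such records tend to be positively correlated, and a test that treats them as independent uses a standard error that is too small.

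The infant comparisons (malformations, and growth at each visit) are exposed to this directly, because infants of a multiple birth enter as separate records. The maternal comparisons are exposed only if a re-enrolled woman is counted per pregnancy.

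This is more than a detail left for a statistical analysis plan. The protocol itself names the tests and itself admits the dependent records. What is at stake is a modest overstatement of precision, and a counting rule that could be settled after the arms are known.

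**Working it through.** **Inputs from Section 10.3.** Mothers: 79 per arm, example 5% against 21%. Infants: 68 per arm, example 1% against 14%. Stated power is at least 80% for each.

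**Assumptions.** Two-sided alpha of 0.05 (the protocol gives no number), a share f of records lying in pairs, and a within-mother correlation r. The protocol gives neither f nor r.

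**Step 1: reproduce the stated power with independent records.** Power = Φ[(d − 1.96·SE0)/SE1], where SE0 uses the pooled proportion and SE1 the two separate proportions.

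- Mothers: SE0 = √(2·0.13·0.87/79) = 0.0535. SE1 = √[(0.05·0.95 + 0.21·0.79)/79] = 0.0520. Power = Φ[(0.16 − 0.1049)/0.0520] = Φ(1.06) = 0.856. Fisher's exact power is 0.830.
- Infants: SE0 = √(2·0.075·0.925/68) = 0.0452. SE1 = √[(0.01·0.99 + 0.14·0.86)/68] = 0.0438. Power = Φ[(0.13 − 0.0885)/0.0438] = Φ(0.95) = 0.828. Fisher's exact power is 0.796.

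The stated figures reproduce; Fisher's test for infants falls just under 80%.

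**Step 2: design effect.** With n records of which fn lie in pairs, there are fn/2 pairs. The variance of a mean or proportion is (σ²/n²)(n + 2·(fn/2)·r) = (σ²/n)(1 + fr). So D = 1 + fr, and the true level of a nominal 0.05 normal-theory test is 2[1 − Φ(1.96/√D)]. Power is recomputed with n/D.

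| f | r | D | True level | Power, mothers | Power, infants |
|---|---|---|---|---|---|
| 3% | 0.3 | 1.009 | 0.051 | 0.852 | 0.825 |
| 5% | 0.3 | 1.015 | 0.052 | 0.850 | 0.823 |
| 10% | 0.3 | 1.03 | 0.054 | 0.845 | 0.817 |
| 10% | 0.5 | 1.05 | 0.056 | 0.838 | 0.809 |
| 20% | 1.0 | 1.20 | 0.074 | 0.786 | 0.754 |

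At D = 1.05 the standard error is too small by a factor √1.05 = 1.025. The last row is an extreme, not an expectation. The formula holds for means as well as proportions, so it also describes the growth t-tests.

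**Step 3: simulated type I error with no arm difference (100,000 trials per setting).**

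| Setting | Test | No pairs | f 5%, r 0.3 | f 10%, r 0.3 | f 10%, r 1 | f 20%, r 1 |
|---|---|---|---|---|---|---|
| Mothers, 10% rate | Chi-square | 0.051–0.052 | 0.054 | 0.055 | 0.063 | 0.078 |
| Mothers, 10% rate | Fisher | 0.028 | 0.029 | 0.031 | 0.036 | 0.045 |
| Mothers, 5% rate | Chi-square | 0.050 | 0.051 | 0.053 | 0.061 | 0.072 |
| Mothers, 5% rate | Fisher | 0.016 | 0.017 | 0.017 | 0.022 | 0.028 |
| Infants, 5% rate | Chi-square | 0.045–0.049 | 0.050 | 0.051 | 0.056 | 0.071 |
| Infants, 5% rate | Fisher | 0.012–0.014 | 0.014 | 0.014 | 0.017 | 0.023 |

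At a 1% infant rate both tests are far below 0.05 in every setting: chi-square at most 0.012, Fisher at most 0.001. Where two values are shown, they come from two runs of the same no-pair setting.

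**Step 4: one twin pair.** A concordant affected pair against no cases is 2/68 = 2.9% against 0/68. The two-sided Fisher p-value is 2·C(68,2)/C(136,2) = 2·2278/9180 = 0.50. Counted per pregnancy, the same pair would be 1/67 = 1.5%.

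**The case against.** The strongest reply is that the effect is small and that part of it depends on how Section 10.7 is read. The maternal comparison is a proportion of participants, which may mean that each woman counts once. The GEE cluster is unnamed, so it could be the mother. Fisher's test will often apply at the planning rates of 1% to 10% for mothers and 1% to 5% for infants, and it is conservative enough to absorb the correlation in every setting tried. All of this stands and it limits the size of the point. It does not cover the infant chi-square, logistic and t-test comparisons, for which no passage provides an adjustment.

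Three stronger readings are tempting, and the document does not support them.

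- A reader might infer that the confidence intervals for the primary comparisons are wrong. Section 10.7 plans none explicitly for those comparisons.
- A reader might infer that twins count twice for preterm delivery or growth restriction. Section 10.2.1 lists both as endpoints of the pregnant woman, so a twin pregnancy is one maternal record.
- A reader might infer that one affected twin pair could create a safety signal. Step 4 gives p = 0.50, and two unrelated cases would give the same table.

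A further fair objection concerns the remedy. If the primary analysis were restricted to first pregnancies, with infants collapsed to any affected, it would discard exposures the registry deliberately enrols. It would also change the per-infant prevalence in the second primary objective. That restriction therefore belongs in a sensitivity analysis only.

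**Conclusion.** The point holds as a mild mismatch between the records the protocol enrols and the tests it names. With 3% to 10% of records in pairs and moderate correlation, the design effect is about 1.00 to 1.05. The chi-square level is then about 0.051 to 0.056 instead of 0.05, and power falls by less than two percentage points. Logistic regression and the growth t-tests are affected in the same direction. Fisher's test stayed below 0.05 throughout, including the extreme setting.

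These figures rest on an assumed alpha of 0.05 and on assumed values of f and r. The maternal part also depends on counting a re-enrolled woman per pregnancy. The missing unit of analysis is a defect whatever those values are, because two analysts could form different numerators and denominators from the same data.

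**What to change.** Amend Section 10.7 as follows.

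1. State the counting unit: maternal outcomes once per pregnancy, malformations per infant.
2. Use mother as the cluster in the logistic models, by GEE or robust variance.
3. Use mother as the cluster in every growth comparison, including those at single time points, in place of the plain t-tests. Name that cluster for the first-year GEE.
4. Keep Fisher's exact test for rare outcomes, because a robust variance is unstable with few events.
5. Alongside it, add a sensitivity analysis with one record per mother: her first enrolled pregnancy, counted as affected if any infant is affected.

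The cost is analysis wording and code, slightly wider standard errors and one additional sensitivity analysis. No extra participants, visits or data are needed, and no enrolled pregnancy or infant leaves the main analysis.

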10.2 Study Endpoints

A pregnant woman is defined as a woman meeting the criteria outlined in Section 5.2. Data for the primary and secondary study endpoints will be collected from the pregnant women and the infants born from these women.

10.2.1 Primary Endpoints: Pregnant Women

Consistent with the primary study objectives, the following endpoints will be assessed for pregnant women:

- delivery prior to 37 completed weeks of gestation
- stillbirth or intrauterine fetal demise (≥ 20 weeks)
- spontaneous abortion (< 20 weeks)
- ectopic pregnancy
- intrapartum hemorrhage
- · postpartum hemorrhage
- non-reassuring fetal status
- chorioamnionitis
- hypertensive disorders of pregnancy
- gestational diabetes

intrauterine growth restriction

10.2.2 Primary Endpoints: Infants

Consistent with the primary study objectives, the following primary endpoint will be assessed for infants:

 Major malformations, defined as structural abnormalities with surgical, medical, or cosmetic importance.

10.2.3 Secondary Endpoint: Infants

Consistent with the secondary objectives, the following endpoints will be assessed for infants:

- Weight, length, and head circumference at birth, one month, six months and 12 months.
- HIV-1 drug resistance mutations among infants who acquire HIV-1 infection

10.3 Sample Size

The overall number of participants to be enrolled in this protocol depends on pregnancy rates in the parent studies. At the time Version 2.0 of this protocol was approved, information was available on the number of pregnant women enrolled into MTN-016 from parent protocol MTN-003 (VOICE). Below we summarize the number of MTN-003 participants who were eligible and enrolled in MTN-016. Among 5,029 participants enrolled into MTN-003, 428 (9%) participants reported a pregnancy. Among these, 243 (57%) were eligible for MTN-016 based on two consecutive monthly visits with a positive pregnancy test (Criteria A from Section 5.2). Of these, 195 (80%) were enrolled in MTN-016 based on this eligibility criterion. An additional 17 women were enrolled based on Criteria B, resulting in a total of 212 pregnant women enrolled in MTN-016 from parent protocol MTN-003. A total of 201 infants were eligible for enrollment from MTN-003. Of these, 185 (92%) infants were enrolled into MTN-016.

Sample size estimates for the number of pregnant women and infants expected from future safety and effectiveness studies, such as MTN-020 (ASPIRE), are based on data from MTN-003, since future trial populations are likely to be similar to the MTN-003 trial population. For example, assuming 3,476 women are enrolled into MTN-020, we estimate that there will be approximately 313 (9% of 3,476) pregnant women and 147 (47% of 313) infants eligible for enrollment into MTN-016. This is a conservative estimate as it is difficult to anticipate the number of pregnant women generated by future and other MTN trials. Both MTN-003 and MTN-020 required use of a highly effective method of contraception as a criterion for enrollment. Future trials that do not have this eligibility requirement may have a higher pregnancy rate.

Pregnant women may elect to terminate participation in the parent study, not meet all eligibility criteria, and/or not wish to enroll in this study, or become lost to follow-up in the parent study. Of the 313 women that we estimate will become pregnant during MTN-020, we estimate that approximately 50% of the women will not enroll due to one of the above reasons. This estimate is also based on the enrollment trends for MTN-003. Thus, we estimate that 158 (50% of 313) pregnant women and 136 (92% of 147) infants will enroll into MTN-016 from MTN-020. We will target no more than 5% lost to follow-up of pregnant women and of mother/infant pairs.

In the absence of a contraceptive effect for the active agent or the placebo, we expect the number of enrolled pregnant women to be essentially balanced, resulting in 79 pregnant women per study arm (total n=158). Similarly, the number of enrolled infants should be approximately balanced, producing about 68 infants per study arm (total n=136). The primary objective involves a comparison of the endpoint by parent protocol study arm. Pregnant women are not randomized to study arms, thus it is anticipated that a certain level of imbalance will be present that may decrease power. However, study power estimates were generated assuming an equal number of participants in both study arms.

The overall proportion of pregnancy loss in MTN-003 among women enrolled in MTN-016 was approximately 6%. Since it is anticipated that the additional primary outcomes for pregnant women will range in frequency from 1%-10% in the placebo arm, a plot showing minimum absolute differences of 5%-20% for a sample size of 158 (79 in each arm) with 80% and 90% power is shown below (Figure 1). For example, if a primary outcome were observed in 5% of pregnant women in the placebo arm, then the study would have at least 80% power to detect a minimum absolute difference of 16%.

[figure not shown]

Figure 1: Power estimates for maternal outcomes

Similarly, since major malformations in infants are relatively rare, for the purpose of power calculations, we will conservatively assume that the proportion of major malformations will range in frequency in the placebo arm from 1% to 5%. A plot showing minimum absolute differences of 2% - 15% for a sample size of 136 (68 in each arm) with 80% and 90% power is shown below (Figure 2). For example, if a major malformation were observed in 1% of infants in the placebo arm, then the study would have at least 80% power to detect a minimum absolute difference of 13%.

[figure not shown]

Figure 2. Power estimates for infant outcomes.

10.4 Blinding

Blinding/unblinding processes will be dictated by the parent study protocols. In the event that an Investigator feels that specific product knowledge is necessary to protect participant safety while the parent protocol is still blinded, they should follow the processes outlined in the parent protocol for early unblinding.

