2.3.2 Rationale

Pregnancy safety data is an essential component of the evaluation of all candidate HIV prevention agents intended for use by reproductive age women. In addition to the inevitable early pregnancy exposures that will occur, there are many other compelling reasons for continuing microbicide-specific investigations of safety in pregnancy:

- 1. Among pregnant and post-partum women, sexual activity, including sexual activity with multiple partners, is common. Therefore, women who may become pregnant and post-partum women may be suitable target populations for HIV prevention agent use.
- 2. Data suggest that pregnancy represents a time of heightened risk for the sexual acquisition of HIV.¹³
- 3. If microbicides and/or PrEP become widely available, pregnant women will likely use them with or without evidence of safety. In the absence of safety data, possible recommendations to perform a pregnancy test prior to each use would create a logistical barrier to widespread uptake.

This registry study will be unique, in that it will also capture infant outcomes, including growth, as defined by birth weight and serial measures of length, weight, head circumference, and abdominal circumference in the first year of life. Including these endpoints among the registry data will provide a richer picture of the potential impact of study product exposure on pregnancy and infant outcomes. Potential differences in infant growth patterns between those exposed and unexposed to active study agents are readily measurable and accounted for by secondary objectives in this study. Another unique feature of this protocol is its inclusion of data collected on pregnancy and infant outcomes for participants using placebo study agents. The prospective collection of these outcome data prior to the unblinding of study treatment assignment will build a natural comparison group into the study database. The impact of study product exposure during pregnancy in the presence of HIV-infection is also unknown. While this is likely to be a rare occurrence, it is prudent to measure the potential impact on the prevalence of HIV drug resistance mutations in the plasma of HIV-infected infants.

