4 STUDY DESIGN

4.1 Identification of Study Design

The HIV Prevention Agent Pregnancy Exposure Registry will be a prospective observational cohort investigation of women with exposures to active and non-active study agents in trials investigating candidate HIV prevention agents and the infants resulting from those pregnancies. Parent trial participants should be offered enrollment in the Registry whenever it is determined that there has been an exposure to a study agent during pregnancy.

Optimally, participant mothers will be enrolled in MTN-016 prospectively (prior to the outcome of pregnancy being known). Participant mothers may also be enrolled in the registry after the pregnancy outcome is known, but only up until one year following the date of pregnancy outcome. Sites are encouraged to enroll participants as early in pregnancy as possible to maximize the validity of the data. Further information on planned analyses is available in Section 10.

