4.2 Summary of Major Endpoints

- 1. Pregnancy and delivery outcomes:
 - delivery prior to 37 completed weeks of gestation
 - stillbirth or intrauterine fetal demise (≥ 20 weeks)
 - spontaneous abortion (< 20 weeks)
 - ectopic pregnancy
 - intrapartum hemorrhage
 - postpartum hemorrhage
 - non-reassuring fetal status
 - chorioamnionitis
 - hypertensive disorders of pregnancy
 - gestational diabetes

- intrauterine growth restriction
- 2. Major malformations, defined as structural abnormalities with surgical, medical, or cosmetic importance.¹

Where pregnancy and delivery outcomes are included both in parent protocols and MTN-016, these outcomes will be assessed primarily in the parent protocol. Inclusion and exclusion criteria to be applied for the identification of major malformations will be consistent with those outlined in Holmes, 2001, except that abnormalities may be ascertained up to one year of age. In summary, major malformations will include structural abnormalities meeting the following criteria:

- 1. Having surgical, medical, or cosmetic importance
- 2. Ascertained up to one year of age
- 3. Independently confirmed according to criteria outlined in the MTN-016 SSP Manual

The following will be excluded as major malformations:

- 1. Minor physical features
- 2. Deformities that represent the normal response of fetal tissue to mechanical forces, i.e., atypical body part growth and/or appearance attributable to fetal position and/or pressure of surrounding maternal tissue(s). For example, molding of the skull, also known as positional plagiocephaly, would not be considered a major malformation
- 3. Physical features at birth that are normally present before 37 weeks of gestation
- 4. Findings on prenatal ultrasonography but not on physical examination
- 5. Genetic disorders

These inclusion/exclusion criteria will be applied to reported major malformations to determine their eligibility for inclusion as primary endpoints.

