5.2 Inclusion Criteria: Mother

Individuals who meet the following criteria are eligible for inclusion in the study:

- 1. Able and willing to provide written informed consent to take part in the study
- 2. During participation in a parent protocol, has/had a known confirmed pregnancy, meeting at least one of the following sets of criteria in A or B:
 - A: Two consecutive monthly study visits, at least 14 days apart, with positive pregnancy tests, in the absence of signs/symptoms of miscarriage or participant report of pregnancy termination.
 - B: One or more of the following assessments:
 - Auscultation of fetal heart tones
 - Positive pregnancy test confirmed by clinic staff in the presence of clinically confirmed enlarged uterus
 - Positive pregnancy test confirmed by clinic staff in the presence of missed menses (no menses occurring at least 60 days from the first day of the last menses) by participant report Clinical assessment of fetal movement
 - Demonstration of pregnancy by ultrasound
- 3. Able and willing to provide adequate locator information, as defined in site SOPs

Note: Participants do not have to be currently enrolled or engaged in follow-up in a parent protocol to participate in EMBRACE.

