10.6 Data and Safety Monitoring Analysis

10.6.1 Interim Study Review (ISR) Committee

No Data and Safety Monitoring Board (DSMB) oversight is planned for this observational study, since pregnancy outcome data are assessed by the DSMB in their

review of the parent protocol. If treatment assignment is blinded in the parent protocol, the MTN ISR Committee will conduct interim reviews of study progress (pooled data only), including rates of participant accrual, retention, and assessment of the primary outcomes while the parent protocol is blinded. Additional reviews are anticipated to occur approximately annually following the initial review. At the time of these reviews, or at any other time, the protocol chair in combination with an external MTN reviewer may recommend that the study proceed as designed, proceed with design modifications, or be discontinued. The protocol chair or external MTN reviewer may consider recommending termination of this study if recruitment and retention are lower than targeted, or if study data quality is poor. The MTN-016 protocol leadership team will routinely monitor study conduct and progress (including participant accrual, retention and data quality); see the MTN-016 SSP for additional details. Once results from a parent protocol are unblinded and analyzed, analysis of the primary and secondary outcomes by study arm can be conducted.

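### Section 10.4 gives the registry no masking of its own once a parent trial unblinds, so some malformations may be judged with arm known, contrary to what Section 2.3.2 says

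*Protocol*

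**What the plan says.** Section 2.3.2 lists as a distinctive feature "The prospective collection of these outcome data prior to the unblinding of study treatment assignment", which is to supply a built-in comparison group. Section 10.4 sets the operating rule: "Blinding/unblinding processes will be dictated by the parent study protocols". Its only other content concerns early unblinding for safety, which also follows the parent protocol.

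Other sections set the registry's own timetable:

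- Section 4.1 prefers enrolment before the outcome is known but allows it afterwards, "but only up until one year following the date of pregnancy outcome".
- Section 5.2 adds: "Participants do not have to be currently enrolled or engaged in follow-up in a parent protocol to participate in EMBRACE".
- Section 4.4 ties accrual to network funding, not to any parent trial's unblinding.
- Section 10.1 states: "Infants will be followed for 12 months". Section 4.2 counts malformations found up to one year of age.
- Section 4.2 requires malformations to be "Independently confirmed according to criteria outlined in the MTN-016 SSP Manual". It does not say that confirmation is masked to arm.
- Section 10.6.1 restricts interim reviews to pooled data while the parent is blinded. After parent results are unblinded and analysed, "analysis of the primary and secondary outcomes by study arm can be conducted". Completion of registry follow-up is not a condition.

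**The concern.** The registry's blind ends at an event that the registry does not control and that can precede its own outcome assessment. The statement in Section 2.3.2 is unqualified, and the operating sections do not secure it.

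The endpoint most exposed is major malformation. It depends on whether an abnormality has surgical, medical or cosmetic importance, and on separating it from excluded minor features. Site staff decide what is suspected and photographed, and confirmers then decide what counts. Knowledge of a mother's arm, or of early by-arm results, could shift either decision in one arm more than the other. With so few events expected, a small shift matters. Section 10.7 cautions about differences between the women who become pregnant in each arm, but not about assessment with arm known.

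**Working it through.** The plan gives no figure to reproduce here, so the check is a timeline followed by an illustration.

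**1. Timeline.** Follow-up remaining after unblinding = remaining gestation + 12 months of infant follow-up − lag from pregnancy detection to parent unblinding.

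- Birth at unblinding: no gestation remains, so 12 months of infant examinations follow.
- Pregnancy outcome at unblinding: the mother may still enrol for up to one year (Section 4.1).
- Latest case, assuming detection at 4 weeks and term at 40 weeks: 36 × 7 / 30.4375 = 8.3 months, plus 12 = 20.3 months from detection.

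The lag is not in the protocol. For that latest case:

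| Assumed lag from detection (months) | Follow-up after unblinding (months) |
|---|---|
| 0 | 20.3 |
| 6 | 14.3 |
| 12 | 8.3 |
| 18 | 2.3 |

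The overlap vanishes only when the lag exceeds about 20 months. Section 10.6.1 also speaks conditionally of the parent being blinded. For an unblinded parent, the statement in Section 2.3.2 could not hold at all.

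**2. Number of events.** Section 10.3 expects 68 infants per arm. At an assumed 3% prevalence, within the 1%-5% range used there, 0.03 × 68 = 2.04 cases per arm. One case moves an arm's prevalence by 1/68 = 1.5 percentage points.

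**3. Share of infants affected (assumption).** Suppose births are spread evenly over 24 to 36 months and unblinding comes at the last birth. Infants with a visit still due are then 12/36 = 33% to 12/24 = 50%. If unblinding comes 6 months after the last birth, the share is 6/36 = 17% to 6/24 = 25%. Pregnancies still under way at unblinding would raise it.

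**4. Size of a possible bias (assumption).** Let true prevalence be 3% in both arms, and let confirmation be halved in one arm among the affected share f only. Observed prevalence in that arm is 3% × (1 − 0.5f), so the apparent risk ratio is 1 / (1 − 0.5f).

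| f | Lower-arm prevalence | Apparent risk ratio |
|---|---|---|
| 33% | 2.5% | 1.20 |
| 50% | 2.25% | 1.33 |
| 17% (6-month lag) | 2.75% | 1.09 |
| 25% (6-month lag) | 2.625% | 1.14 |

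In cases, the first two rows lose 2.04 × 0.167 = 0.34 and 2.04 × 0.25 = 0.51 of an expected case in that arm.

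**The case against.** **The bias needs facts that are not shown.** These are when the parent unblinds, whether site examiners then learn individual arms, and whether confirmers see arm. The parent protocols and the SSP Manual may settle all three. Analysing a parent trial by arm does not by itself tell an examiner which arm a given mother was in. This stands: a reader might infer that malformations will be assessed unmasked, but the protocol shows only that they may be. A masking rule in the SSP Manual would help, yet masked confirmers cannot recover a finding that a site never reported.

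**Section 2.3.2 is rationale.** A reader might take it to make collection before unblinding the guarantee of a valid comparison. It says only that a natural comparison group will result, and Section 4.1 openly permits later enrolment. The sentence therefore needs a qualifier, but it remains a factual statement that the operating rules do not secure.

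**Safeguards exist.** Section 4.2 lists explicit exclusions and independent confirmation. Appendix III sets out the components of the neonatal examination, Section 7.14 requires an experienced clinician, and Section 9.2 covers care or referral for any infant with abnormal findings. Pregnancy and delivery outcomes shared with the parent are assessed primarily there. These points narrow the concern mainly to malformations. None of them masks arm.

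**A sensitivity analysis is ordinary SAP content.** Its absence from the protocol is not a fault. It is proposed as part of a remedy for Section 10.4.

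**By-arm analysis is permitted, not scheduled.** A reader might want it barred until the last Month 12 visit. The documents do not support going that far: the registry has no DSMB of its own, and a bar would delay arm-specific safety data by up to about a year. Keeping early results from those who examine and confirm deals with the bias more directly.

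**Conclusion.** The concern holds as a gap between Section 2.3.2 and the operating rules. Enrolment, infant examination and malformation confirmation can run up to about a year past a birth or pregnancy outcome that falls at parent unblinding, and Section 10.4 gives no masking for that period. Bias is possible, not certain.

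The apparent risk ratio of about 1.2-1.33 under no true effect is an illustration. It assumes 3% prevalence, 33-50% of infants affected, halved confirmation among them in one arm, and no lag before unblinding. The halving has no basis in the documents. The calculation also treats every malformation in an affected infant as assessed after unblinding, although some of these infants will already have had their newborn, Month 1 and Month 6 examinations.

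A reader might infer a spurious risk ratio of 2 (3.0% against 1.5%). That would require halved confirmation of every case in one arm, which does not fit an affected share of 33-50%.

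The risk is to the estimate more than to the test. Even a larger difference, 3% against 5% with 68 per arm, would reach two-sided 5% significance by Fisher's exact test only about 2% of the time. The change is worth making because it is cheap and masking cannot be restored afterwards.

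**What to change.** - **Section 10.4:** state that those who confirm malformations receive records and photographs without arm, whatever the parent trial's blinding status, until that parent's EMBRACE data are locked.
- **Data collection and analysis:** record whether each enrolment, and each malformation's first report, came before or after parent unblinding. Run a sensitivity analysis that excludes those that came after.
- **Section 10.6.1:** leave by-arm analysis permitted, but state that results produced before that parent's registry follow-up is complete are not shared with site examiners or confirmers.
- **Section 2.3.2:** qualify the statement so that it claims collection before unblinding only where that is the case.

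The cost is protocol wording, a check that material sent for confirmation carries no arm, minor extra data handling and one extra analysis. By-arm results need not be delayed.
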